HCO ₃	Amount of bicarbonate in the arterial blood. This is used to aid in diagnosis of metabolic acidosis or alkalosis.	mmol/L
PaO ₂	Partial pressure of oxygen in the arterial blood. This is the true measure of O ₂ build in the blood.	mmHg
PaCO ₂	Partial pressure of carbon dioxide in the arterial blood. This is the true measure of CO ₂ build up in the blood, and reflects whether the lungs are keeping up in expelling the extra CO ₂ from abdominal absorption.	mmHg
End tidal CO ₂	The level of carbon dioxide in the air exhaled from the body, as measured by the ventilator. Essentially, this reflects the amount of CO ₂ that the lungs are expelling due to CO ₂ absorption from the insufflations. This increases over the course of the procedure.	mmHg
"Blunted" end tidal CO ₂	A technical observation made regarding the shape of the end tidal CO ₂ curve on the capnogram displayed on the ventilator. This is an observation, not discretely measureable.	N/A
Tidal volume	The lung volume representing the normal volume of air displaced between normal inspiration and expiration when extra effort is not applied (i.e., normal/resting breathing).	ml
O ₂ saturation	Measure of how much oxygen the blood is carrying as a percentage of the maximum it could carry.	%
Pneumoperitoneal pressure	Measurement of air or gas in the abdominal (peritoneal) cavity.	mmHg
Peak inspiratory pressure (PIP)	Point of maximal airway pressure.	mmHg
Positive end-expiratory pressure (PEEP)	Pressure maintained in airways at end of exhalation.	mmHg
Smoke evacuation quality	Smoke evacuation occurs during surgical procedures where there is tissue ablation. Smoke evacuation systems capture the plume (smoke comprised of carbonized cell fragments, water vapor, and hydrocarbons) from vaporized tissue near its origin before it becomes air-dispersed and deposits in the respiratory tracts of the surgical team.	Categorical (see Appendix B)

2.0 - METHODS

2.1 - Study Population

Adult male patients \geq 18 years of age with prostate cancer who are eligible and electing to undergo robotic prostatectomy surgery at OhioHealth Dublin Methodist Hospital between March 1, 2016 and February 28 2017 (12 months). Exclusion criteria to robotic surgery include:

- 1) Cirrhosis or liver failure (Child-Pugh class A, B, or C) or clinical suspicion of liver failure
- 2) Ascites
- 3) Uncontrolled diabetes [as reported by the pre-anesthesia testing (PAT) physician]

4) Renal insufficiency (serum creatinine level > 3.0 mg/dl)

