Exclusion criteria to participation in this study include:

- 5) Age < 18
- 6) Emergency surgery
- 7) Persons not capable of providing informed consent
- 8) Persons participating in any other research study involving an investigational drug or device or investigational surgical procedure that could interfere with the physiologic parameters being collected (for example, a study evaluating different anesthesia regimens that could confound study results).
- 9) Non English-speaking

2.2 - Hypothesis

It is hypothesized that the AirSeal® System will allow for lower CO₂ absorption rates than the Xcel® System. Furthermore, lower variance in pneumoperitoneal pressure will allow for less "over-pressure" events and peritoneal stretch, which may reduce postoperative pain. Pain will therefore also be assessed through self-report and post-operative pain medication usage (see Table 4 & Appendix A), and analyzed in comparison between both groups.

The term "over pressure" refers to times when the measured pressure in the peritoneal cavity exceeds the set pressure on the insufflator. In such cases, the standard insufflation systems will stop the flow of CO₂ into the abdomen through the port and will actively vent gas to reduce the pressure back to the set point (usually 10mmHg with a maximum of 20mmHg). This "over pressure" theoretically should not occur with the AirSeal® system because the lack of a valve on the port allows gas to escape immediately when the pressure rises (e.g. abdominal muscle contractions when anesthesia is light) so that the pressure does not exceed the set level. "Peritoneal stretch" refers to stretching of the peritoneum (lining of the abdominal wall) from insufflation of the abdomen. The higher the pressure of the pneumoperitoneum/intra-abdominal pressure, the more stretch there will be of the peritoneum with potentially more postoperative pain.

We intend to analyze the results of a total of 100 patients randomized to either the AirSeal® system or conventional trocars.

2.3 - Study Variables & Outcomes of Interest

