The following data points are all routinely collected for patients who choose to undergo robotic prostatectomy, via the OhioHealth electronic medical record, CareConnect. We will collect similar data points for patients electing enrollment in this trial which include the following listed below (Tables 2-4). Data points which are not collected in the standard of care setting are noted below in **bold face type**. Only the study staff will have access to the database created solely for use in this study. Data will be de-identified following study completion, prior to statistical analysis.

Table 2. Study Variables by Operative Time-point

(a) Preoperative data [collected at the preoperative office/clinic visit, in the office setting, or in

the pre-anesthesia testing (PAT) office visit]:

- 1) Medical record number
- 2) Patient name
- 3) Patient date of birth
- 4) Phone number
- 5) Email address
- 6) Body mass index (BMI)
- 7) Weight (lb)
- 8) Medical history
- 9) Surgical history (major only)
- 10) Serum creatinine (most recent prior to surgery) (mg/dl)
- 11) Hemoglobin (g/dl)
- 12) Preoperative pain measured by the NRS-11 (Appendix A)**

(b) Intraoperative data:

- 1) Details of the surgical procedure
- 2) The number, size(s), and locations of ports used (standard protocol vs. deviation from standard protocol)
- 3) Values obtained from anesthesia report at baseline, 60 minutes after insufflations, and at the end of procedure and mean and standard deviation calculated from continuously recorded values:
 - a) End tidal CO₂ (mmHg)
 - b) O₂ saturation (%)
 - c) Respiratory rate
 - d) Blood pressure
 - e) Heart rate
 - f) Tidal volume (ml)
 - g) PIP (peak inspiratory pressure) (mmHg)
 - h) PEEP (positive end-expiratory pressure) (mmHg)
- 4) CO₂ absorption rate via arterial blood gases (ABGs) at baseline, 60 minutes after insufflations, and at the end of the procedure [PaCO₂ (mmHg), HCO₃ (mmol/L) & PaO₂ (mmHg)]
- 5) Number of times the anesthesiologist intervenes to adjust ventilation settings throughout the surgery to prevent the values from elevating further once they reach 37-38 mmHg
- 6) Estimated blood loss (EBL, in ml)
- 7) Core body temperature (after trocar placement, at 30 minutes, at 60 minutes, and at end of procedure; Fahrenheit)
- 8) Insufflation time (minutes)

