- 9) Insufflation pressure at which the procedure was performed (mmHg), and the total number (#), magnitude(s) (% increase in mmHg), and time(s) (hh:mm) of increased pressure episodes necessary to successfully complete the procedure
- 10) Procedure time (minutes from initial incision to closure)
- 11) Pneumoperitoneal pressure ranges (mmHg)**

12) Smoke evacuation quality at the end of surgery (1-Below Average; 2-Average Amount; 3-Above Average) (Appendix B)
 
13) Number of times significant loss of pneumoperitoneum occurs (#), timepoint, and level of pressure adjustment (mmHg)
 
14) Scope cleanings (#)
 
15) Malfunctions of the AirSeal® System or control devices (# times)
 
16) Total amount of gas used during the procedure (liters)

(c) Postoperative data collected in the PACU through discharge:
 
1) Postoperative pain by the NRS-11 at multiple time points (Appendix A)
 
2) Postoperative parameters (as recorded by the PACU nurses as standard of care)
 
a) O₂ saturation (%)
 
b) Time in PACU (post anesthesia care unit) (hours)
 
c) Post-operative nausea and vomiting (presence/absence)
 
d) Vital signs (HR/RR/BP/temp) – first recorded in PACU setting
 
e) Use of post-operative pain medication (ketorolac, Percocet, Tylenol Extra Strength), recorded as the total daily morphine equivalent dose (“MED”, in mg/day)
 
3) Incidence of wound infection
 
4) Length of stay (targeting same day or next day discharge; 0 to 2)

(d) Postoperative data collected through postoperative Day 1
 
1) Postoperative parameters (standard of care)
 
a) Vital signs (HR/RR/BP/temp) – first recorded in non-PACU setting
 
b) Use of post-operative pain medication (ketorolac, Percocet, Tylenol Extra Strength), recorded as the total daily morphine equivalent dose (“MED”, in mg/day)
 
2) Serum creatinine (mg/dl)
 
3) Hemoglobin (g/dl)
 
4) Urine output (ml; 1900-0700 hours postoperatively)
 
5) Incidence of wound infection

For item (b)2, a deviation from the standard port number/size(s)/locations would be due to body habitus, and will not have an effect the clinical outcomes for the patient. We will collect information on all surgical outcomes that occur until discharge from the PACU. The average amount of time spent in the PACU is roughly 1-2 hours. There will be no extended or long-term follow-up.

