Standard operative procedures will be followed regardless of randomization sequence or participation in the study (e.g., standard of care procedures). If a technical malfunction of the AirSeal® iFS or AirSeal® Access Port were to occur, the surgeon would replace both with a conventional insufflator and trocar. Documentation of the AirSeal® malfunction will be made and the subject will be followed for safety purposes, but no further study data will be recorded. All ports will be placed according to standard care. All clinical decisions will be made per standard practice and policy. One trocar per patient will be randomized between the Endopath and AirSeal® trocars. The other trocars used for the procedure will be standard (5 standard plus 1 randomized for a total of 6) and will not vary for patients on the study as compared with typical robotic prostatectomy patients.

A standardized anesthesia regimen will be followed in order to create a uniform population. The anesthesia regimen is typical for this type of surgery. Subjects will be given midazolam (2.0 mg) for pre-induction. Fentanyl (up to 1.5 mcg/kg), propofol (up to 2.0 mg/kg) and rocuronium (as needed for neuromuscular blockade) will be used for anesthesia. Anesthesia will be maintained with sevoflurane and/or deflurane and oxygen. Fentanyl (2-3 mcg/kg/hr or 0.7 mcg/kg boluses) will also be used for anesthesia maintenance. A dose of ondansetron (4 mg) will be given for nausea and vomiting prophylaxis and a dose of ketorolac (15-30 mg) will be given for pain prophylaxis. Glycopyrrolate and neostigmine will be used for anesthesia reversal. Postoperatively, ketorolac, oral Percocet, and/or Tylenol Extra Strength (ES) will be given as needed to treat pain. Ondansetron will also be given as needed for nausea control.

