Aim #3) Compare pain scores through discharge from the preoperative and post-anesthesia care units (PACU) by monitoring self-reported pain ratings using an 11-point numerical rating scale (NRS-11) and pain medication usage via morphine equivalent dose (MED) units.

To evaluate our this outcome we will use a linear mixed model with pain score as the dependent variable and treatment group and time as independent variables. Mixed models are often preferred over a two-way ANOVA because they allow for incomplete data from participants and do not require a strictly normal distribution in the dependent variable. We will also examine the difference in MED units between groups using a t-test. Statistical significance will be set at p<.05.

[figure not shown]

3.0 - REFERENCES

- 2) McCarus SD, et al. Gynecological laparoscopy: improving laparoscopic herniation outcomes without trocar site fascial closure: a multicenter trial. Presented at: American College of Surgeons 90th Annual Clinical Congress; October 10-14, 2004: New Orleans, LA.
- 3) Ethicon Endo-Surgery. "Endopath Xcel Bladeless." *Xcel Bladeless*. Endopath, 2010. Web. 18 Sept. 2012. <<http://www.ethiconendosurgery.com/xcelbladeless>>.
- 5) A new Valve-Less Trocar for Urology Laparoscopy: Initial Evaluation. *Journal of Endourology* 2009;23: 1535-39.
- 6) Herati et al. Use of the valveless trocar system reduces carbon dioxide absorption during laparoscopy when compared with standard trocars. *Urology* 2011; 5: 1126-1130.

4.0 - APPENDICES

A. Numerical Rating Scale (NRS-11)

Pain monitoring schedule by RN in PACU using NRS-11.

Timepoint	Definition
Baseline	Prior to surgery
Post-operatively	After surgery & after anesthesia completion

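### Aim 3 compares postoperative morphine-equivalent dose without recording or adjusting for preoperative opioid use, which costs precision but does not bias the comparison

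*Combined protocol and SAP*

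**What the plan says.** **Who can enrol.** Section 2.1 admits adult men "with prostate cancer who are eligible and electing to undergo robotic prostatectomy surgery". Criteria 1-4, under "Exclusion criteria to robotic surgery include", cover liver disease, ascites, uncontrolled diabetes and renal insufficiency. Criteria 5-9, under "Exclusion criteria to participation in this study include", cover age, emergency surgery, capacity to consent, interfering studies and language. None mentions opioids, other analgesics or chronic pain.

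**What is recorded before surgery.** Table 2(a) in section 2.3 has twelve items. The two nearest to analgesic history are "8) Medical history" and a preoperative NRS-11 pain score. Neither gives a dose.

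**What is measured after surgery.** Table 2(c) and (d) list "Use of post-operative pain medication (ketorolac, Percocet, Tylenol Extra Strength), recorded as the total daily morphine equivalent dose", in mg/day. Section 2.4 makes the use demand-driven: "Postoperatively, ketorolac, oral Percocet, and/or Tylenol Extra Strength (ES) will be given as needed to treat pain". No rule says whether an opioid continued from home counts.

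**How it is analysed.** Section 2.5, Aim 3: "We will also examine the difference in MED units between groups using a t-test". A general rule at the start of section 2.5 adds adjustment for baseline characteristics that differ significantly between the groups.

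**The concern.** Section 2.2 uses postoperative pain medication as a read-out of pain from peritoneal stretch. A man already taking opioids may need more as-needed analgesia for the same surgical pain because he is tolerant. If his home opioid is counted, his total also contains drug he would have taken anyway. Either way, part of the between-patient spread in MED has nothing to do with the trocar.

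The plan shows that it cares about such noise, since section 2.4 standardizes the anesthetic regimen to make the patients more alike. It also treats the two Aim 3 measures unequally: the pain score has a preoperative value, while MED has none. At stake is the precision of the MED comparison and its exposure to an uneven split of a few high users.

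**Working it through.** **Inputs from the documents.** The total is 100 patients (section 2.2) and the significance level is 0.05 (section 2.5). The plan gives no power, effect size or SD, so there is no plan figure for MED to reproduce.

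**Assumptions.** 1:1 allocation (50 per arm); two-sided test; MED SD of 15 mg/day in opioid-naive men; a share p = 3-8% of preoperative users; d = 30-60 mg/day extra postoperative MED per user. None of these is stated in the documents.

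**Step 1: variance.** If users have a mean d higher than other men, the variance is 15² + p(1-p)d². The SE ratio is the square root of that variance over 225, and the information left is 100 divided by the squared ratio.

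| p | d (mg/day) | Variance | SE ratio | 100 patients are worth |
|---|---|---|---|---|
| 3% | 30 | 225 + 0.0291 × 900 = 251.2 | 1.06 | 90 |
| 5% | 60 | 225 + 0.0475 × 3600 = 396.0 | 1.33 | 57 |
| 8% | 60 | 225 + 0.0736 × 3600 = 490.0 | 1.48 | 46 |

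**Step 2: chance imbalance.** Two extra users at +60 mg/day in one arm move its mean by 2 × 60 / 50 = 2.4 mg/day. The SE of the arm difference among opioid-naive men is 15 × √(2/50) = 3.0 mg/day, so this shift is 0.8 SE, or 2.4 / (3.0 × 1.48) = 0.54 of the most inflated SE. From exact binomial probabilities with 50 per arm, the arms differ by three or more users in 7% of trials at p = 2%, 24% at 5% and 40% at 10%.

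**Step 3: power.** With 50 per arm, a difference of (1.96 + 0.84) × √(2/50) = 0.56 opioid-naive SDs has 80% power if nobody is a user. Let users exceed other men by k such SDs, so that the variance is multiplied by 1 + p(1-p)k². Without adjustment, power at 0.56 SD becomes:

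| p | k = 1 | k = 2 | k = 3 |
|---|---|---|---|
| 2% | 79% | 77% | 73% |
| 5% | 78% | 73% | 65% |
| 10% | 76% | 67% | 55% |

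In this model, a covariate that captures the users' excess returns the residual variance to the opioid-naive value, and power to about 80%.

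**Step 4: bias.** Simulating the t-test with no treatment effect (40,000 trials in each of four settings, p = 5-20%, k = 2-3) gave type I error between 4.8% and 5.1%. The test keeps its nominal level.

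**Step 5: the existing adjustment rule.** It cannot act on a variable that is not recorded. If any/no preoperative use were recorded, a baseline test at 0.05 would be significant in about 1% of trials at p = 2%, 4% at 5% and 5% at 10%. Most imbalances would stay unadjusted.

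**The case against.** A reader might infer that pre-treated men bias the comparison, so that their opioid use passes for a device effect. The documents do not support this. Allocation is randomized, the expected arm difference is unaffected, and the t-test's own SE already contains the extra variance. The illustrated 2.4 mg/day shift is under one SE, so it is ordinary sampling noise.

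A reader might also infer that MED necessarily contains the home dose. The definition names only three postoperative drugs, given as needed. A home opioid other than Percocet might never be counted, so that part depends on a counting rule that the plan does not state. The tolerance part does not depend on it.

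It is also fair to say that every figure for size is assumed, and that the 48% needs both upper ends at once. The data collection forms (Appendix C) and tool (Appendix D) are not in the text available, and medical history could be taken to include medication. Even so, section 2.5 names no such variable as a covariate. Finally, section 1.2 makes PaCO₂ the primary observation, so this is a secondary matter.

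What survives is narrower: an identifiable source of variance is neither listed for collection nor prespecified for adjustment.

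**Conclusion.** The point holds as a minor loss of efficiency in one of the two Aim 3 measures. Men taking opioids before surgery are eligible, no preoperative dose is listed, and as-needed MED is compared without adjustment. Under the assumed SD of 15 mg/day, 3-8% users and 30-60 mg/day extra use, the SE of the MED difference rises by about 6-48%. The effect is small if few users enrol, and the documents do not say how many to expect. It is not a validity problem, and it does not touch Aims 1 and 2. Nor does it justify excluding men on opioids: that would narrow the whole trial for the sake of one secondary measure, when a covariate can recover most of the precision.

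**What to change.** 1. Add to Table 2(a): preoperative opioid dose (MED, mg/day), taken from the medical record.
2. State in Table 2(c) and (d) whether an opioid continued from home counts in postoperative MED.
3. In section 2.5, Aim 3, replace the t-test with a linear model of MED on treatment group, with preoperative opioid dose (or any/no use) as a prespecified covariate, whether or not the groups differ significantly at baseline. There is no need to subtract the preoperative dose as well: once it is a covariate in the linear model, subtracting it leaves the treatment estimate unchanged.

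Leave eligibility as it is. The cost is one extra data field and slightly more analysis, with no change to treatment. The gain is small if few men use opioids.

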As stated earlier, if a technical malfunction of the AirSeal® iFS or AirSeal® Access Port were to occur, the surgeon will replace both with a conventional insufflator and trocar. This is the same procedure that would take place should a technical malfunction occur with conventional insufflator and trocar. If the surgeon decides that the operation is not feasible with a standard insufflator and trocar (loss of insufflation/inconstant pressure with bleeding or anesthesia problems), then the surgeon can replace the standard insufflators with the AirSeal® iFS or AirSeal® Access Port. These events will be documented should they occur.

Patients will undergo standard insufflation (filling of the peritoneal cavity with CO₂ gas). After trocar placement, initial insufflation will be performed to 6mmHg in all patients. All procedures will be performed as per standard technique. If required, insufflation pressures will be increased up to 15mmHg per standard surgeon protocol. Increased insufflation pressure will be maintained either transiently (\leq 5 minutes to control bleeding or to improve access/visualization) or for the duration of the procedure as per surgeon need. The amount of time at each insufflation pressure will be measured. Procedures in which $<5\%$ of the case are performed above 8mmHg will be considered "low impact" procedures. We will compare CO₂ absorption rates between high pressure (>8mmHg) and low impact (\leq 8mmHg) procedures in the final analysis.

Study subjects will also be removed from the study if they revoke their informed consent. If, in the opinion of the surgeon/investigator, clinical observations made during the study suggest it may be unwise to continue, the surgeon/investigator may stop the study. In the event that the investigator chooses to discontinue or terminate the study, appropriate notification will be given to the IRB and sponsor.

The principal investigator also has the right to remove any subject from the study. Reasons for which a subject may be removed from the study include:

- Occurrence of a serious or intolerable adverse event
- The subject requests to be discontinued from the study
- Non-compliance with medication, protocol violation or unreliable behavior
- A protocol violation sufficiently serious as to require subject withdrawal
- Emergence of a clinically significant change in a laboratory parameter(s)

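### Study recording stops after an AirSeal malfunction, the control-arm rule is unclear and no analysis population is named, so between-arm comparisons can lose data because the test device failed

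*Combined protocol and SAP*

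**What the plan says.** **AirSeal malfunction.** Section 2.4 has the surgeon replace the AirSeal unit and port with conventional equipment. After that, "the subject will be followed for safety purposes, but no further study data will be recorded".

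**Conventional malfunction.** Later in Section 2.4 the replacement rule is repeated, followed by: "This is the same procedure that would take place should a technical malfunction occur with conventional insufflator and trocar". The sentence does not say whether the data stop is part of that procedure.

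**Control switched to AirSeal.** If the surgeon finds the operation not feasible with standard equipment, "then the surgeon can replace the standard insufflators with the AirSeal® iFS or AirSeal® Access Port". On data, the text adds only: "These events will be documented should they occur".

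**Commitment to collect outcomes.** The text below Table 2 in Section 2.3 says that surgical outcomes will be collected up to discharge from the PACU, and makes no exception for device failure.

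**Who is analysed.** Section 2.2 says: "We intend to analyze the results of a total of 100 patients randomized". Section 2.5 names no analysis population and does not say in which arm, or with what data, a replaced or switched case is analysed. Nor does any section say whether data recorded before a malfunction enter the analysis. The only remark on incomplete data in Section 2.5 concerns the mixed model for pain.

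**Malfunction count.** Table 2(b) provides for recording "Malfunctions of the AirSeal® System or control devices (# times", but no expected rate is given.

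**The concern.** The stop is triggered by something that happens after randomisation: failure of the device under test. The patients who leave the data set are therefore not a random subset of the AirSeal arm.

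Operative time shows the difficulty most directly. Replacing a device plausibly lengthens the operation, and those are the operations whose time would drop out of the study data. If failed cases do worse and control data are complete, the as-randomised comparison is tilted towards AirSeal. If the stop also covers failed or switched controls, the tilt can cancel or reverse.

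Even with few failures, the plan allows different data sets to be built from the same trial. One analyst could drop failed cases, another could use their partial data, and a third could move switched controls to the other arm. That choice should be made before outcomes are seen by arm.

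**Working it through.** **1. Which comparisons are touched.** Section 2.5 plans six between-arm outcome tests. For a malfunction during the operation, under the Section 2.4 stop:

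| Outcome | Planned test | Effect on the study data set |
|---|---|---|
| Operative time | t-test or Wilcoxon | Removed: Table 2(b) defines "Procedure time (minutes from initial incision to closure" |
| Smoke rating | chi-square | Removed: "Smoke evacuation quality at the end of surgery" |
| MED | t-test | Removed: postoperative |
| Pain (NRS-11) | linear mixed model | Of the five Table 4 scores only baseline remains; the 8-hourly scores mentioned below Table 4 also go |
| Anesthesiologist interventions | Poisson or zero-inflated | Cut short |
| Maximum pressure | t-test or Wilcoxon | Possibly cut short; the maximum may already have occurred |

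The end-of-procedure blood gas is lost too, but the CO₂ changes under Aim 1 are described, not tested.

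**2. Inputs for an illustration.** From the documents: 100 patients in total and significance at p<.05. Assumed: 50 per arm (no allocation ratio is stated), two-sided testing, 1 to 7 AirSeal failures (2% to 14% of 50), failed cases *d* = 1 SD worse than the rest of their arm, whole cases dropped, and a null of equal as-randomised means. The calculation is for a comparison of two means, so it fits operative time or MED. It does not represent the chi-square, Poisson or mixed-model tests. The plan gives no effect size, SD or power behind N = 100, so there is no figure of its own to reproduce.

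**3. Formulas.** With *k* AirSeal and *c* control cases lost:

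- shift = *d*(*k* − *c*)/50
- SE = √(1/(50 − *k*) + 1/(50 − *c*))
- type I error = P(|Z + shift/SE| > 1.96)

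**4. Results.**

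| *k* | *c* | *d* | shift (SD) | SE | type I error |
|---|---|---|---|---|---|
| 1 | 0 | 1 | 0.02 | 0.201 | 5.1% |
| 7 | 0 | 1 | 0.14 | 0.208 | 10.3% |
| 7 | 0 | 0.5 | 0.07 | 0.208 | 6.3% |
| 7 | 7 | 1 | 0 | 0.216 | 5.0% |
| 7 | 3 | 1 | 0.08 | 0.211 | 6.7% |
| 1 | 7 | 1 | −0.12 | 0.209 | 8.9%, now against AirSeal |

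**5. Cost of analysing as randomised.** With 50 per arm, 80% power corresponds to an effect of 2.80 × √(2/50) = 0.56 SD. If *k* switched patients get no device effect, this becomes 0.56 × (1 − *k*/50):

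- one switch: 0.549 SD, power 78.4%
- seven switches: 0.482 SD, power 67.3%

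Excluding those patients instead gives 79.6% and 76.9%, but gives up the randomised comparison.

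**The case against.** **Much of the data still exists.** Section 2.3 describes the listed items as routinely collected unless marked in bold, and postoperative pain medication is listed as standard of care. Section 2.4 says that anesthesia-machine values upload automatically. This stands. A reader might infer that all six outcomes are irretrievably lost, but what stops is study recording. The clear permanent losses are the smoke rating, which the surgeon gives on a study form, and the end-of-procedure blood gas.

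**Earlier data.** A reader might assume that values recorded before the malfunction are kept and analysed. No section says so; the stop addresses only further recording.

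**The 10.3% depends on the null.** With equal as-randomised means and failed cases 1 SD worse, functioning AirSeal cases are truly 0.14 SD better than controls. If instead functioning AirSeal equals control and the harm comes from the replacement itself, dropping failures leaves the error at 5%. This also stands: the figure is an error rate only for an as-randomised question, which the plan never specifies.

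**Direction.** The failure counts and the 1 SD are not from the documents, and the scenarios run from favouring AirSeal, through none, to disfavouring it.

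**What remains.** These points limit the size of the problem and do not remove the rule. The Section 2.2 statement about 100 randomised patients gives no handling for replaced cases. The mixed-model remark covers pain only, and a patient with only a baseline score adds almost nothing to the postoperative contrast.

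**Conclusion.** The concern holds as a flaw in the data rule and a gap in the analysis plan, and should be fixed. Two commitments in the document conflict, failed and switched controls are unresolved, and no analysis population is defined. Missing data are therefore made to depend on failure of the test device.

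Confidence is high on the text and low on the consequence. A reader might infer that the trial is biased towards AirSeal with a doubled type I error; the documents do not support that, because they give no malfunction rate and leave control handling open. Under the stated assumptions the range is 5.1% to 10.3% when only AirSeal data stop, and 5.0% with equal loss in both arms. One malfunction is negligible.

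**What to change.** **Section 2.4, data rule.** Replace the data stop with wording such as: *All scheduled study data continue to be recorded after any device replacement or switch, in either arm, unless the subject withdraws consent. A replacement or switch is not in itself a reason to stop data collection.*

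**Reconcile.** Bring three places into line with this rule: the outcome-collection commitment below Table 2 in Section 2.3, the Section 2.4 text on conventional malfunctions and switched controls, and the Section 2.4 removal list. The list includes protocol violation, which a switch might be judged to be, so state how data are handled for removed subjects. The rules on when to replace a device or remove a subject stay unchanged.

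**Section 2.5.** Add:

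- The primary analysis includes all randomised patients in their assigned arm.
- The intervention count and maximum pressure cover the whole procedure.
- Sensitivity analyses exclude malfunction or switched cases.
- Malfunctions, switches and removals are reported by arm.

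**Cost.** This is a change of wording plus modest extra recording, since machine data upload automatically and nurses already take pain scores. The statistical price is dilution: for a 0.56 SD effect, as-randomised power falls from 80% to 78% with one switch and 67% with seven. Reporting the exclusion analyses alongside shows how much this matters.
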